11.0 PROJECT TIMELINE	
APPENDIX 1: FLOWCHART FOR THE COLLECTION OF SPECIMENS	

1.0 Background and rationale

In India, sentinel surveillance is used annually to estimate the prevalence of Human Immunodeficiency Virus (HIV) infection in the country and to monitor trends in the epidemic. Sentinel surveillance for HIV in India began in 1994, at 55 sentinel sites, under the National AIDS Control Program-I (1992–1999). The population groups and sites for HIV sentinel surveillance are selected based on information about the risk behavior of various risk groups for HIV infection. The high-risk groups of the population include patients attending sexually transmitted disease (STD) clinics, female sex workers, injecting drug users (IDUs), and men who have sex with men (MSM); a low-risk group of the population includes women attending antenatal clinics. The rationale for selecting sentinel sites in the clinics attended by these subgroups of the population is that blood samples are collected from the people who attend the clinics for various purposes, and the samples can be tested for HIV in an unlinked anonymous manner. Since 1994, the number of sites in the sentinel surveillance system has been increasing. In 2002, sentinel surveillance was conducted at 384 sites and in 2003, at 455 sites.

Despite the HIV, Sexually Transmitted Infection (STI) and risk behavior surveillance activities currently underway in India, there are considerable gaps in the information available to understand both the course of the epidemic as well as the STI correlates and behavioral risks that fuel it. To measure the major outcomes and impacts of the interventions funded by the Bill & Melinda Gates Foundation (BMGF) under the Avahan India AIDS Initiative (Avahan), the existing surveillance system must be strengthened and expanded. A robust surveillance system will allow BMGF and its governmental and nongovernmental partners not only to follow key trends in HIV, STIs and risk behaviors, but also to use the data to project trends into the future.

The purpose of this assessment is to gather data for impact monitoring and evaluation of the Avahan India AIDS Initiative funded by the BMGF in 71 districts of 6 States and five highway sites. The proposed mapping, size estimation and integrated behavioral and biological assessment (IBBA) will provide some of the key data needed to assess major outcomes and impacts of the interventions funded by BMGF. This is the first independent impact-level evaluation of this scale of targeted interventions with sex workers and clients, high risk men and IDUs on HIV/AIDS. The project will be implemented in close collaboration with National AIDS Control Organization (NACO) and State AIDS Control Societies (SACS) and will provide valuable information to feed back into and strengthen the National AIDS Control Program in India.

The IBBA will be conducted three times during the five-year project period of Avahan. The baseline assessment will be undertaken in 2005, mid-line in 2007 and end-line in 2009. This protocol aims to cover the baseline, mid-line and end-line assessments.

2.0 Objectives

The overall objective of the IBBA is to collect necessary information for assessing the outcomes and the impact of HIV interventions in Avahan project districts. In addition, conduct of the IBBA will strengthen the capacity of national and state level institutes including The Indian Council of Medical Research (ICMR), the National AIDS Research Initiative (NARI), The National Institute of Epidemiology (NIE), The National Institute of

Nutrition (NIN), the Regional Medical Research Council (RMRC), and the National Institute of Medical Statistics (NIMS).

The specific objectives of the IBBA are to collect the following data in selected districts of the Avahan project states of Andhra Pradesh, Maharashtra, Tamil Nadu, Karnataka, Manipur and Nagaland and along the National Highways:

1. To measure the major outcomes and impacts of the interventions funded by the Bill & Melinda Gates Foundation (BMGF) under the Avahan India AIDS Initiative by collecting behavioral and biological trend data in populations targeted by the interventions.
2. To make available data that will be used for estimating sizes of populations targeted by the project.
3. To make information available to a partner organization under Avahan for modeling the impact of the intervention.

3.0 Methods

3.1 IBBA populations:

[figure not shown]
The populations that will be included for mapping, size estimation and IBBA are:

Five Avahan States: Tamil Nadu, Andhra Pradesh, Maharashtra, Nagaland, Manipur

- Female Sex Workers Brothel Based (FSW-BB)
- Female Sex Workers Non-Brothel Based (FSW-NBB)
- Male Who Have Sex With Men (MSM)/Male Sex Workers (MSW)
- Male clients of Female Sex Workers
- Male Injecting Drug Users (IDU)

National Highway

- Truckers Drivers and helper (TD/H)
- Female Sex Workers Highway-Based (FSW-HB)

3.1.1 Operational Definitions of IBBA Populations

Female Sex Workers: (Definitions will vary by state/district to match with Avahan program)

- Female Sex Workers (FSW):** Females aged 18 years or older, either brothel or non-brothel based, who sold sex in exchange for cash at least once in the past one month.
- Female Sex Workers Brothel-Based (FSW-BB):** Females aged 18 and years or older working/living/operating in brothels in red light/brothel areas (to be specified for each district) that have been paid cash in exchange for sex at least once in the past month.
- Female Sex Workers Non-Brothel Based (FSW-NBB):** Females aged 18 years or older, soliciting male clients on the street or in other non-brothel settings, who sold sex in exchange for cash at least once in the past one month.
- Service Bar Based Female Sex Workers (FSW-DSBB):** Females aged 18 years or older, soliciting clients in service (“free service”) bars, who sold sex in exchange for cash at least once in the past one month.
- Female Sex Workers Highway-based:** Females aged 18 and over who are highway-based, who have been paid cash in exchange for sex at least once in the past month.

Clients of FSWs: Men aged 18 years or older recruited from red-light districts and other commercial sex access points that have paid cash in exchange for sex with a female at least once in the past one month.

Injecting Drug Users: Males aged 18 years or older that have injected drugs for non-medical reasons any time during the past six months.

Men who have sex with men (Definitions will vary by state/district to match Avahan definitions)

a. Male Sex Workers: Males aged 18 years or older who sold sex to other males in exchange for cash (cash/kind in some places) at least once in the past three months. (Hijras/eunuchs to be sampled separately).

b. Men who have sex with men: Males aged 18 years or older who exchanged (bought or sold) sex in exchange for cash (or cash/kind) at least once in the past three months.

Truckers and helpers: Men aged 18 years or older driving trucks or assisting drivers along inter-state transport routes.

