3.3 Sample Sizes

3.3.1 *Measuring Changes in Behaviors and documenting STI Prevalence*

Sample sizes for each population sub-group included in the IBBA have been calculated on the basis of the following factors typically used in surveys with probability samples:

1. the expected baseline value of key behavioral indicators (e.g. consistent condom use with various partner types)
2. magnitude of change it is desired to be able to detect;
3. confidence level;
4. statistical power; and
5. design effect.

The following formula was used to determine the sample size for target groups for the IBBA:

$$n = D \frac{\left[\sqrt{2P(1-P)}Z_{1-a} + \sqrt{P_1(1-P_1) + P_2(1-P_2)}Z_{1-b} \right]^2}{\Delta^2}$$

Where:

D = design effect;

P_1 = the estimated proportion at the time of the first survey;

P_2 = the proportion at some future date, such that the quantity $(P_2 - P_1)$ is the size of the magnitude of change it is desired to be able to detect;

$$P = (P_1 + P_2) / 2;$$

$$Z_2 = (P_2 - P_1) / \sqrt{P(1-P)}$$

$Z_{1-\alpha}$ = the z-score corresponding to the probability with which it is desired to be able to conclude that an observed change of size $(P_2 - P_1)$ would not have occurred by chance;

$Z_{1-\beta}$ = the z-score corresponding to the degree of confidence with which it is desired to be certain of detecting a change of size $(P_2 - P_1)$ if one actually occurred.

For the IBBA, the following assumptions have been made regarding these parameters:

1. Expected baseline value: 50%. Measurements require the highest sample size to detect change when the baseline is 50%, hence this figure was used. If it can be safely assumed that baseline values of all indicators are significantly lower or higher, then sample sizes could be lowered.
2. Desired change to detect: 10-15%. This refers to the amount of change that can be detected between two survey rounds. For example, if condom use changed by an absolute 10-15%, this would be detected as a statistically significant change. A lower absolute change would not be detected as statistically significant. Smaller differences require larger sample sizes.
3. The alpha level has been set at 0.05, corresponding to 95% confidence in the observed estimates.
4. The beta level has been set at 0.10, corresponding to 90% power.
5. Design effect: 1.7 for time-location sampling and 1.5 for RDS. This adjusts for the use of sampling designs that are not simple random methods, e.g. cluster sampling.

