Minimum sample size requirements per sub-population per district to measure both differences between groups and changes over time at the levels of significance and power indicated above are summarized in the table below. These numbers will be adjusted upward after the pilot test to account for anticipated non-response (refusal and duplication).

Justification for IBBA sample sizes for key sub-populations

IBBA Population	Indicator	Expected baseline value	Change to Detect	% in denominator	Design Effect	Required sample size	Sample size (rounded off) required for the IBBA
1. FSW Brothel based	Consistent condom use with clients	50%	15%	ALL	1.7 TLS	385	400
2. FSW Non-brothel based	Consistent condom use with clients	50%	15%	ALL	1.7 TLS	385	400
3. FSW Highway based	Consistent condom use with clients	50%	15%	ALL	1.7 TLS	385	400
4. Male Sex Worker/MSM	Consistent condom use with clients	50%	15%	ALL	1.5 RDS	339	400
5. Injecting Drug User	Consistent use of safe injecting equipment	50%	15%	ALL	1.5 RDS	339	400
6 Clients of FSW (Male bridge group)	Consistent condom use with FSW	50%	15%	ALL	1.7 TLS	385	400
7. Truckers	Consistent condom use with FSW	50%	15%	65%	1.7 TLS	592	600

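### Where MSM definition (b) is used, row 4 of the sample-size table cannot assume that every respondent has clients; at n = 400, 90% power then needs about 85% of respondents to have sold sex

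*Protocol*

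**What the plan says.** Protocol section 3.1.1 gives two definitions under the heading for men who have sex with men, with the remark "Definitions will vary by state/district to match Avahan definitions".

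- Definition (a), male sex workers: "Males aged 18 years or older who sold sex to other males in exchange for cash" (cash or kind in some places), in the past three months.
- Definition (b), MSM: "Males aged 18 years or older who exchanged (bought or sold) sex in exchange for cash (or cash/kind) at least once", with a three-month recall period. The partner's sex is not stated.

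The table in section 3.3.1 merges the two groups in the row "4. Male Sex Worker/MSM", whose entries read "Consistent condom use with clients 50% 15% ALL 1.5 RDS 339 400". The indicator is thus condom use with clients, the whole sample is taken to be in the denominator, 339 are required and 400 are planned.

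The same table reduces the denominator for truckers to 65% and raises their requirement from 385 to 592. The only later increase that the section names is for refusal and duplication.

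**The concern.** A respondent can contribute to an indicator on condom use with clients only if he has clients. Under definition (a) every respondent has sold sex to males, so the full denominator is right. Under definition (b) a man who has only paid for sex is eligible and is interviewed, but falls outside the indicator. The effective sample is then smaller than the table assumes. The inflation for refusal and duplication does not restore it, because it replaces interviews that were not obtained or were repeated, not interviews of men without clients.

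At stake is the stated ability to detect a 15-point change between rounds in this one indicator, in districts that use (b). HIV and STI prevalence are unaffected, because men who only bought sex still contribute to them.

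The missing partner sex is a separate wording gap in the same definition. Read literally, (b) also admits a man who paid only women. Any such man would lower the share of respondents with clients further.

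**Working it through.** **Inputs (Protocol section 3.3.1).** Baseline P1 = 0.50 ("Expected baseline value: 50"%). Change 15 points, so P2 = 0.65 and P = 0.575. "The alpha level has been set at 0.05, corresponding to 95% confidence in the observed estimates". "The beta level has been set at 0.10, corresponding to 90% power". Design effect D = 1.5 for respondent-driven sampling (RDS) and 1.7 for time-location sampling (TLS).

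**Step 1: reproduce the plan's figures.** The protocol's formula is

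n = D × [z_α √(2P(1−P)) + z_β √(P1(1−P1) + P2(1−P2))]² / (P2−P1)²

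With z_α = 1.960 and z_β = 1.2816:

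- first term: 1.960 × √0.48875 = 1.3702
- second term: 1.2816 × √0.4775 = 0.8856
- (1.3702 + 0.8856)² / 0.0225 = 226.16 before the design effect
- row 4: 226.16 × 1.5 = 339.2 (plan: 339)
- TLS rows: 226.16 × 1.7 = 384.5 (plan: 385)
- truckers: 384.5 / 0.65 = 591.5 (plan: 592)

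The figures reproduce with the two-sided 1.96. A one-sided z would give 276 for row 4.

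**Step 2: break-even share.** Let f be the share of respondents who sold sex. The total required is 339.2/f under RDS.

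- RDS: 400 suffices if f ≥ 339.2/400 = 84.8%.
- TLS: 400 suffices if f ≥ 384.5/400 = 96.1%.

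TLS is included because section 3.2.2 lets the method for this group vary by state, although row 4 and section 4.1.1 anticipate RDS.

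**Step 3: power at the planned 400.** The effective size per round is m = 400f/D, and

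power = Φ[(0.15√m − 1.3702) / 0.6910], where 0.6910 = √0.4775.

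Example, f = 0.65 and D = 1.5: m = 173.3, (0.15 × 13.166 − 1.3702)/0.6910 = 0.875, power 0.81.

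The protocol gives no value of f, so the rows below are assumptions.

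| Share who sold sex | In denominator | Power, RDS (1.5) | Total needed for 90%, RDS | Power, TLS (1.7) |
|---|---|---|---|---|
| 100% | 400 | 94% | 340 (plan rounds to 339) | 91% |
| 90% | 360 | 92% | 377 | 88% |
| 85% | 340 | 90% | 400 | 86% |
| 75% | 300 | 86% | 453 | 82% |
| 65% | 260 | 81% | 522 | 76% |
| 50% | 200 | 70% | 679 | 64% |

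**Step 4: detectable change at 400.** Solving the formula for the change at 90% power under RDS gives 13.9 points at 100% sellers, 15.9 at 75%, 17.1 at 65% and 19.3 at 50%.

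**Step 5: dependence on the baseline.** The same formula with D = 1.5 gives 304 for 60% to 75% (break-even 304/400 = 76%), 241 for 70% to 85% (60%) and 346 for 40% to 55% (87%). The 85% threshold therefore belongs to the protocol's 50% baseline.

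**The case against.** The strongest reply is that the plan has slack. It interviews 400 against a requirement of 339, which is 18% more, so under RDS about 15% of respondents can be outside the denominator before power drops below 90%. Under definition (a) nobody is outside it. The definitions are also expressly left to vary by state and district, and nothing says where (b) will be used. All of this stands, and it makes the point conditional.

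Three stronger readings are tempting and are not supported:

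- **That the stated power is missed.** This needs (b) to be in use and the seller share to be below about 85% (96% under TLS). The protocol states neither. The truckers' 65% is a precedent for the method, not an estimate for this group: truckers are defined by occupation alone, whereas both MSM definitions require commercial sex.
- **That the MSM sample overlaps the sample of clients of female sex workers.** The heading and label of (b) imply male partners, and section 4.2.1 asks about buying and selling among males with other males. The omission is a gap in an eligibility criterion, not a demonstrated overlap.
- **That a shifting mix of buyers and sellers biases the trend.** Men who only bought sex drop out of an indicator on clients, so its denominator contains sellers only. What can vary between rounds and sites is its size, and hence its precision.

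The reply does not remove the inconsistency between definition (b) and a full denominator. The table corrects for exactly this in the trucker row and not here.

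**Conclusion.** The point holds conditionally. Wherever definition (b) is used, a denominator of all respondents is unjustified for an indicator on clients, and the stated 15-point change at 90% power then rests on an unstated seller share. At the protocol's 50% baseline that share must be at least about 85% under RDS, or about 96% under TLS. If it were 75%, 65% or 50%, all of which are assumed values, power under RDS would be 86%, 81% or 70%. Where definition (a) is used, the row and its power stand. The missing partner sex in (b) is a wording defect to be corrected at the same time. Severity: should-fix, conditional on (b) being used.

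**What to change.** 1. In section 3.1.1, state in definition (b) that the partner is another male, as definition (a) does.
2. In section 3.3.1, split row 4 by definition. Keep the full denominator for (a). For (b) sites, enter an expected seller share in the column for the percentage in the denominator, as for truckers, give its source or mark it as an assumption, and use the design effect of the sampling method chosen there.
3. For (b) sites, restate power or detectable change at 400: under RDS, about 17 points at 65% sellers and about 19 points at 50%.

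Moving (b) sites to an indicator that pools paid and paying partners would also make the full denominator true. It would change what is measured, however, so it is not needed for this correction.

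The cost is one phrase in a definition and one extra table row. The questionnaire already covers buying and selling among males, and no respondents are added. The downside is a somewhat less favourable stated figure for (b) sites. The change belongs before the baseline round, because later rounds are compared with it.

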3.1.2 Protection of vulnerable subjects

Recruitment of these high-risk populations requires addressing the clandestine, socially marginalized nature of these groups and the behaviors that they engage in. To protect participants who may be vulnerable to coercion or undue influence the following general procedures will be adhered to. These procedures will have added specificity as this protocol is contextualized for each site.

- Access to these groups may require going through various gatekeepers such as employers, brothel owners or police. Discussions with employers will clarify the purpose of the IBBA, e.g. STI detection and treatment, STI counseling, condom distribution and obtaining information to guide improved implementation of ongoing projects. Employers will be made aware that all data forms will have no names, with exception of the consent form which will not be linkable to any of the behavioral or biological data, and that participation by all individuals will be voluntary and through random recruitment. While these employers might be used to gain access, they will not be utilized for any component of recruitment and no information regarding recruitment will be given to these intermediaries. Sites where employers appear to be coercive will be excluded from the IBBA
- Specific efforts will be undertaken to inform the NGOs working with the populations targeted by the IBBA, as well as community leaders, about the purpose, risks and benefits of the IBBA. Prior to recruitment, information about the IBBA will be shared through educational sessions with NGOs and other partners. At these educational sessions the IBBA will be explained and questions answered. These educational sessions will stress the voluntary nature of the IBBA and their importance in tracking progress in reducing HIV transmission.
- IBBA participants will be protected through a voluntary written consent process, with the option of witnessed verbal consent for those who are not comfortable with written consent. All IBBA documents and specimens will be labeled with only a unique respondent number with the exception of the consent form, which will not be linkable to any of the other IBBA documents or data. Prior to recruitment, two IBBA staff will explain the IBBA procedures in detail to potential participants in a private room, and answer all questions. They will emphasize that participation is voluntary and should participants decide not to participate or withdraw from the IBBA at any time, their

decision would not affect any services from the NGO or the clinic that they would normally receive. The IBBA staff will administer written or witnessed verbal informed consent depending on the preference of the participant.

- The IBBA is anonymous. The participant's signature on the consent form is in no way linked to the person's behavioral and biological data since the unique respondent number does not appear on the consent form. No names or personal identifiers will be recorded. All questionnaires and biologic specimens will be labeled with the respondent number. The assessment participant will be given a card with his/her unique respondent number as a way to return for syphilis results and free syphilis treatment, (with the exception of those referred to the Avahan supported Population Services International (PSI)As there are no identifiers there is no way to trace any positive laboratory tests or to determine who chose to participate or not participate in the assessment.
- The IBBA Project staff, India Council of Medical Research (ICMR), FHI and community monitoring boards will closely monitor the consent procedure.
- Discussions will be held between ICMR, National AIDS Research Institute (NARI), FHI, IBBA and Avahan project staff and community leaders on potential impact of data and appropriate release of the data when the IBBA is complete.

3.1.3 Key behavioral and biological indicators

Behavioral Indicators

- Sexual risk behavior including number and type of sex partners ("commercial", "regular" and "non-regular")
- Condom use with different types of sex partners
- Other practices related to condom use and safe sex
- Knowledge of STIs and STI care-seeking behaviors
- Knowledge and attitudes toward HIV/AIDS
- Drug and substance use (including injecting and equipment sharing)
- Mobility and migration patterns influencing sexual behavior and risk
- Perception of HIV and STI risk
- Exposure to Avahan and other HIV/AIDS prevention interventions

Biological Indicators

- STI prevalence (syphilis serology, *N. gonorrhoeae* (Ng), *C. trachomatis* (Ct), herpes simplex virus (HSV) 2 serology, HBC and HCV in IDUs, and for those reporting ulcers *T. pallidum* (Tp), *H. ducreyi* (Hd) and HSV-2 antigen detection)
- HIV prevalence
- HIV incidence (BED-CEIA validated for Indian sub-type C)

3.2 Site and Respondent Selection

3.2.1 Selecting Project Districts for Mapping, Size Estimation and IBBA

Presently Avahan is working in approximately 75 districts across six states of India, 19 districts in Andhra Pradesh, 20 in Karnataka, 16 in Maharashtra, 4 in Manipur, 4 in

Nagaland and 12 in Tamil Nadu. Based on the recommendation of a the WHO M&E Advisory Group for the IBBA, it was decided that the IBBA would be carried out in approximately 29 project districts, 8 in Andhra Pradesh, 5 in Karnataka, 6 in Maharashtra, 2 in Manipur, 3 in Nagaland and 5 in Tamil Nadu. In addition, five segments of the National Highway would also be part of the IBBA.

For selecting the IBBA districts within states, two key criteria were considered: (i) socio-cultural region (SCR); and (ii) size of the female sex worker (FSW) population, or, in the case of Manipur and Nagaland, size of the injecting drug user (IDU) population. Specifically, the requirement was to have representation from each of the different SCRs within a state to ensure heterogeneity in terms of social, economic and cultural characteristics. Then within each SCR the criterion was to select the districts with the highest number of persons at high risk (FSWs and IDUs). A third criterion, prevalence of antenatal clinic (ANC) attendees in the district was originally proposed to fulfill the objective of obtaining a mix of higher and lower prevalence districts. However, in the end, this criterion did not play a role because there were only a handful of cases where more than one district was selected within an SCR, and in those cases, after considering the size of the risk population, there was not much significant difference in terms of ANC prevalence. It is recognized that the size of the risk populations (FSW and IDUs) is fluid and that attempts to enumerate these populations at any given point in time will yield different results. However, since a probability-based method was not being used to select districts, the primary concern was to try to select the districts with the highest concentrations of at-risk populations. The proposed method adequately addresses this need.

